1. STUDY OBJECTIVES

1.1 Primary Objectives

Hypothesis 1: FORT-A will result in significantly greater improvements in pain management among PRC Veterans compared to standard PRC care based on the primary outcome measure of self-report disability (Oswestry Disability Index) at both short- (pre- to post-treatment) and long-term (6/12-month) follow-up.

Hypothesis 2: FORT-A will also result in significant improvements on secondary pain management outcomes compared to PRC, including pain coping (intensity/ cognitions), emotional distress (depression, PTSD, anxiety), and objective disability (functional capacity, gait) at short- and long-term follow-up.

Hypothesis 3: We hypothesize that FORT-A will result in significantly lower rates of opioid recidivism compared to standard PRC treatment based on timeline followback interview at 12-months follow-up.

Hypothesis 4: We also hypothesize that FORT-A will result in significantly less opioid recidivism compared to PRC treatment based on secondary measures of opioid medications including Medication Event Monitoring System (MEMS), pill counts, and consultation with prescribing providers/ documentation in the VA Electronic Health Record (CPRS).

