The secondary outcome (addressing AIM2) for this research is rate of opioid medication recidivism. In consultation with study co-I and opioid dependence/misuse expert, [name], we decided to adopt a conservative definition of recidivism of use of any opioid for three days in any 30-day period. This definition was chosen (instead of a non-abstinent definition as described in McCabe et al., 2013) because this medical population may include veterans given short-term opioid therapy for a new injury or surgery and we did not want to count that as relapse or recidivism to opioid use. As was the case for disability, opioid use will be assessed through objective (MEMS caps) and subjective (timeline followback interview; TLFB) methods. Because some participants may shift patterns of other pain medication use as a result of discontinuing opioids, we will also complete TLFB for other pain medications and ask participants to use MEMS for their “most helpful” pain medication (if they are not taking an opioid med). All opioid medication use will be measured with MEMS and TLFB. We will also assess pain medication using the Medication Quantification Scale – III (MQS). The MQS was developed through the American Pain Society as a standardized method of quantifying pain medication use along dimensions of drug class, drug dose, and drug detriment (Harden et al., 2005). Both TLFB and MQS data will be gathered monthly (at all assessment intervals in person) and during monthly reminder phone calls. Previous studies have shown that Timeline Followback interviews demonstrate the best reliability and validity for long-term medication use (Kunoe et al., 2009), so TLFB was chosen as the focal secondary outcome measure for this research.

[figure not shown]

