Ongoing Assessments	MEMS/Actiwatch – Start at pre-treatment and end at 12-month f/u TLFB/MQS – Administered at pre- and post-treatment and every month after post-treatment.	
----------------------------	---	--

Study evaluators will maintain active logs for assessments identifying participants by unique ID # only and including date of evaluation, whether or not evaluation was in a study window, if PI approved out of window assessment (when outside of a window), whether an AE was identified in the assessment (e.g., suicidal ideation on the PHQ-9 item #9), and notes about assessment (see **Appendix F**). These logs will be monitored by the PI and coordinator weekly to ensure that assessments are completed on time. An example assessment log is as follows:

ID	Assessment	Assessment Domains	Assessment Date	Window? (Approved?)	Notes
10EX1	Pre-Treatment * within 2 wks before tx phase	Psychosocial	01/01/2001	Y	Treatment Phase Start 01/04/2001 End 01/25/2001 10EX1 forgot MEMS and Actiwatch at Post-Tx; PI approved out of window download; we can use data up to 01/25/2001 10EX1 sustained injury playing basketball on 07/20/2001; not cleared for FCE for 3 months; PI denied out of window assessment due to injury delay 10EX1 completed FCE on 01/24/2002 but not time for testing; r/s for when returns from vacation (01/24); PI approved out of window
		FCE	01/01/2001	Y	
		TLFB	01/01/2001	Y	
		MEMS	01/01/2001	Y	
		Actiwatch	01/01/2001	Y	
	Post-Treatment * within 2 wks after tx completed	Psychosocial	01/25/2001	Y	
		FCE	01/25/2001	Y	
		TLFB	01/25/2001	Y	
		MEMS	02/10/2001	N (Y)	
		Actiwatch	02/10/2001	N (Y)	
	6-Month *24 weeks ± 2 weeks after tx completed	Psychosocial	07/22/2001	Y	
		FCE	---	N (N)	
		TLFB	07/22/2001	Y	
		MEMS	07/22/2001	Y	
		Actiwatch	07/22/2001	Y	
	12-Month *50 weeks ± 2 weeks after tx completed	Psychosocial	02/07/2002	N (Y)	
FCE		01/24/2002	Y		
TLFB		02/07/2002	N (Y)		
MEMS		01/24/2002	Y		
Actiwatch		01/24/2002	Y		

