6.2.4 Followup Visits (see Figure 4)

Follow-up assessments will occur in the following intervals:

Visit	Measure	Assessment Window
Visit 2 (Baseline)	Psychosocial Assessment Pain Diary Functional Capacity Evaluation (FCE) Upload Actiwatch Provide and Train for MEMS Adverse Events Opioid/Medication Assessments (TLFB/SOWS/COMM/Concomitant Medications) MQS STRONG STAR Common Data Elements	≤ 2 weeks before treatment
Visit 14 (Post-Treatment)	Psychosocial Assessment Pain Diary FCE	≤ 2 weeks after treatment

	Upload Actiwatch Upload MEMS Adverse Events Opioid/Medication Assessment MQS STRONG STAR Common Data Elements	
Phone Assessments 1-11	Opioid/Med Assessment (TLFB) MQS	Monthly ± 1 week
Visit 15 (Six-Month Follow-Up)	Psychosocial Assessment Pain Diary FCE Upload Actiwatch Upload MEMS Adverse Events Opioid Assessment/Medication MQS STRONG STAR Common Data Elements	± 24 weeks after treatment ± 2 weeks

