6.2.5 Completion/Final Evaluation

List each assessment to be performed at the participant's final visit.

Visit 16 (One-Year Follow-Up)	Psychosocial Assessment Pain Diary FCE Upload Actiwatch Upload MEMS Adverse Events Opioid/Medication Assessment (including CPRS and PAT) MQS STRONG STAR Common Data	± 50 weeks after treatment ± 2 weeks
----------------------------------	---	---

	Elements Exit Interview	
--	----------------------------	--

All participants will be asked to complete all final assessments, regardless of whether or not they complete the study. After completing the intervention, we will maintain monthly telephone contact with all participants to promote adherence to follow-up assessments and to give them an opportunity to report any adverse events they may have experienced since finishing the three-week intervention phase. This monthly contacts will also include monthly administration of the TLFB for pain medication and opioid medications and administration of the MQS. We will also use these monthly calls to identify and troubleshoot any potential problems with the Actiwatch or MEMS Caps.

Participants who were lost to contact at any point before the 12 month follow-up assessment will be contacted to complete the Missing Data Assessment, ODI, TLFB and Concomitant Meds Form. Participants will be mailed a letter explaining why they are being contacted, how long the phone interview will take, and what information we will collect. The letter will also include opt-out information. Within two weeks of the participants receiving this letter, we will contact participants to discuss whether they would like to participate. The Missing Data Assessment is a 4-item measure of global symptom improvement of pain, perception of satisfaction and burdensomeness of study treatments, and reason(s) for discontinuing study participation. This assessment will be used to assess missing data randomness and to categorize participants who discontinued study participation as a way to help impute missing data and improve future studies with these treatments in similar populations.

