Medication Data will be adjudicated by the PI, the Research Coordinator, and [name] (an expert in trauma and addiction comorbidity). Timeline followback interview and MQS-III data will be discussed for each participant by the IE and the Coordinator within two business days of each assessment. If there are any noted problems with the TLFB data, then the assessment will be adjudicated by the above sub-committee within 2 days of review. MEMS cap data will be gathered for each participant's reported "most helpful" pain medication and any opioid medications they are prescribed by VA or other providers outside the VA system during the course of the study. MEMS data will be downloaded for each participant at each assessment follow-up visit. Upon download, the IE will scrutinize downloaded data to ensure that it falls within an expected range. If aberrant or missing data are noted, these will be adjudicated with the above sub-committee (and potentially discussed with the manufacturer if hardware or software problems are suspected) in a deidentified format.

The primary opioid endpoint will be the timeline followback (TLFB) interview. The TLFB represents the primary measure of opioid use because of its reliability and sensitivity as a daily measure of opioid use and its lack of perceived stigma compared to regular urine tox screen. A trained and masked IE will administer TLFB asking participants about any opioid medication use and use of other medications for pain. The TLFB Interview for this study was adapted from Sobell and Sobell (1992) as a semi-structured clinical interview asking the participant to use a blank calendar to describe the number of pain pills taken each day for 30 days. Instructions are provided to help the interviewer guide the participant in completing the recall as accurately as possible. This method has been reliably used in other trials of medication/opioid use and abuse (Kunoe et al., 2009).

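### The schedule does not deliver the MEMS and pill-count measures of opioid recidivism named in Hypothesis 4

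*Combined protocol and SAP*

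**What the plan says.** Section 3 presents MEMS as the objective counterpart to the TLFB and says that "All opioid medication use will be measured with MEMS and TLFB". Hypothesis 4 in Section 1.1 tests recidivism on "secondary measures of opioid medications including Medication Event Monitoring System (MEMS), pill counts", prescriber consultation and CPRS documentation. The Precis defines recidivism as use of any opioid on three or more days in any 30-day period.

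On procedure:
- The visit table in 6.2.4 lists "Provide and Train for MEMS" at baseline only. The post-treatment, six-month and one-year visits list uploading only.
- Section 5.4 runs MEMS continuously: "Start at pre-treatment and end at 12-month f/u".
- Under Section 3, a participant not taking an opioid puts the cap on the pain medicine that he or she finds most helpful.
- Section 9.5.2 adds "any opioid medications they are prescribed by VA or other providers outside the VA system during the course of the study", and states that "MEMS data will be downloaded for each participant at each assessment follow-up visit".
- Section 6.2.5 says of the monthly contacts: "We will also use these monthly calls to identify and troubleshoot any potential problems with the Actiwatch or MEMS Caps".
- Pill counts appear in none of the schedules in 6.1, 6.2.4 and 6.2.5, and are not among the medication outcomes in 9.5.2.

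TLFB, given monthly, is the primary opioid measure (Sections 3 and 9.5.2). CPRS and the state program, Prescription Access in Texas (PAT), are read at the one-year visit (9.5.2).

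**The concern.** A MEMS cap records openings only of the bottle it is on. Criterion 6 in Section 4.1 requires at least one opioid-free week before the program, so the expected starting position is a cap on a non-opioid bottle. A participant who later returns to opioids does so from a new bottle. That bottle can be capped only once the opioid is known and a cap has reached the participant, and by then three days of use may have passed.

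Two kinds of use fall outside MEMS whatever the timing. One is opioids that the participant does not declare. The other is opioids that were not prescribed, because 9.5.2 covers prescribed opioids only while the definition covers any opioid.

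Section 9.6 gives no rule for MEMS data, and nothing separates time without a cap on an opioid from time without opioid use. If uncapped time were scored as abstinence, MEMS recidivism would be biased downward, and agreement or disagreement with TLFB could not be interpreted. This matters because TLFB is self-report from participants who, as Section 9.2 acknowledges, cannot be masked.

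**Working it through.** The documents give no figure for MEMS capture, so there is none to reproduce. The calculations below are illustrative.

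**1. Inputs.** Post-treatment is at Week 4 to 5 and the six-month visit at Week 30 (6.1), so the gap is (30 − 5) × 7 = 175 days. Phone contacts are monthly, taken as a gap of 30 days. The threshold is 3 days. Assumptions not in the documents: one new opioid course of L days, a start date uniform over the gap g, and a cap fitted at the end of the gap.

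**2. Share of courses in which MEMS logs at least 3 days.** The course must still have 3 days to run when the cap arrives, so the share is (L − 3)/g, with a maximum of 1.

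| Cap added | 10-day course | 30-day course |
|---|---|---|
| At the next visit (g = 175) | 7/175 = 4% | 27/175 = 15% |
| On the day of a monthly call (g = 30) | 7/30 = 23% | 27/30 = 90% |

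Longer courses fare better. In the visit-only case a 90-day course gives 87/175 = 50%, and the share reaches 100% at L = 178 days.

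**3. Second check, with a different window and a weaker criterion.** Starts are uniform over the 350 days after treatment (50 weeks × 7), and the result is the share of courses leaving no MEMS record at all.

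| Cap supply | 3 days | 7 days | 14 days | 30 days | 90 days |
|---|---|---|---|---|---|
| At the 24- and 50-week visits only | 98% | 96% | 92% | 83% | 49% |
| Same day as a monthly call | 91% | 78% | 56% | 6% | 6% |
| 7 days after a monthly call | 100% | 100% | 78% | 28% | 6% |

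For example, with visit-only caps a 14-day course leaves a record if it spans either visit: 2 × 14/350 = 8%, so 92% leave none. With 11 monthly calls and same-day caps, 11 × 14/350 = 44%, so 56% leave none. If a spare cap were given at baseline, or a cap issued at dispensing, the loss for prescribed opioids could be near 0%. The documents do not say which case applies.

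**4. Reach of the dispensing records.** PAT holds 365 days (9.5.2). Under 5.4 and 6.2.5 the one-year visit is at 50 ± 2 weeks after treatment, or 336 to 364 days, so the look-back just reaches the end of treatment. Section 6.1 instead allows ± 2 weeks around 12 months post-treatment. Taking 12 months as 365 days, the latest visit is at 365 + 14 = 379 days, and the first 14 days after treatment are lost. Section 5.4 also allows approved out-of-window visits.

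**The case against.** The strongest reply is that the gap is one of silence. Section 9.5.2 plainly intends to cap opioids prescribed during the study. Nothing in 6.2.4 limits a participant to one cap. Table 6.1 marks MEMS at baseline and at every later assessment visit, and lists it among the purposes of the monthly phone contact. A spare cap at baseline would close most of the gap for prescribed opioids. This stands to the extent that a reader might infer that MEMS cannot measure recidivism at all, and the documents do not support that. What remains is that no passage says who issues a cap, when, or on what trigger.

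A reader might also infer that MEMS would show almost no recidivism in either arm whatever happened. That does not follow, because 30-day courses are mostly caught under monthly capping and half of 90-day courses even under visit-only capping. Criterion 6 enrols people with at least three months of earlier persistent use, so a return to sustained use is plausible. Near-zero counts in both arms would in any case show no difference, not support for FORT-A.

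Nor is it right to infer that the trial has no objective check. CPRS is already in Hypothesis 4, and PAT is read at one year; both can show prescriptions that a participant did not declare.

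Finally, it cannot be assumed that every participant is off opioids at baseline. Criterion 6 counts its week back from the program, whereas baseline may be up to two weeks before treatment. Section 3 (recent and ongoing use), the 6.2.1 screening table (persistent use over the past three months) and Section 8 (some participants may choose to stop) all sit awkwardly with criterion 6.

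**Conclusion.** The concern holds in a bounded form. The Section 3 statement that all opioid use will be measured with MEMS is not backed by the schedule, and the pill counts in Hypothesis 4 have no schedule at all. MEMS-based recidivism would be undercounted: short courses are the most exposed, and undeclared or non-prescribed use is not captured. Under the assumptions stated, MEMS would log three or more days in about 4% to 23% of 10-day courses and 15% to 90% of 30-day courses. These ranges rest on assumed cap timing and course length, and a baseline supply of spare caps would change them greatly for prescribed opioids. The pill-count omission and the mismatch between prescribed opioids and any opioid rest on no such assumption.

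The consequence is confined to Hypothesis 4. A reader might infer that the main Aim 2 result is compromised, but Hypothesis 3 and the Aim 2 analysis rest on monthly TLFB, and the primary ODI outcome is untouched.

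**What to change.** - In 1.1, 3 and 9.5.2, make the planned dispensing records (CPRS plus PAT) the main objective measure for Hypothesis 4. Score them from dispensing date and days' supply against the protocol's own definition of three or more days in any 30-day period, and label the result *opioid obtained*. A rule of any opioid dispensed would abandon that definition.
- State that PAT's 365-day look-back may not reach the end of treatment when the one-year visit is late, and mark the unobserved days as missing.
- Narrow the Section 3 statement on all opioid use to the prescribed opioids covered by 9.5.2.
- Record the issue date of any cap placed on an opioid. Use MEMS only from that date, as a supporting measure of persistence, and never score uncapped time as no use.
- Delete pill counts from Hypothesis 4 or schedule them.
- Reconcile Section 3, criterion 6 in 4.1, the 6.2.1 screening table and Section 8 on opioid status at entry.

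The cost is mainly wording, plus extracting dates and days' supply from records already due to be read at one year. The downside is that dispensing is not ingestion, and dispensing records miss non-prescribed opioids too, so TLFB should stay the primary measure of use.

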4. SELECTION AND ENROLLMENT OF PARTICIPANTS

Participants for this research will include (N=130) U.S. military Veterans treated through the South Texas Veterans Health Care System (STVHCS) for chronic musculoskeletal pain associated with deployment to OEF/OIF/OND (see *Inclusion/Exclusion Criteria* below). Eligible Veterans can have multiple pain concerns, but their primary pain concern must be musculoskeletal pain. All eligible Veterans must be a prior persistent opioid user who was removed from their opioid medication by their VA provider. Participants will be recruited through the STVHCS Polytrauma Clinic, the STVHCS Pain Management Service, and the STVHCS Primary Care Service. They will be eligible for care in the PRC. Our PRC partners estimate that they enroll approximately 30 new patients at the PRC per month, roughly 80% of whom would meet criteria for this research. We will recruit through direct provider referrals and advertisements posted in VHA clinics; both of these strategies have been quite successful in both the original FORT trial and our ongoing STRONG STAR research efforts. Our PRC collaborators ([name] and [name]) will ask their staff to introduce the study to new PRC patients and will be available to answer questions. This research has been adopted as a STRONG STAR initiative, and will have access to STRONG STAR resources and procedures for recruitment. This will be of significant benefit because STRONG STAR studies routinely achieve their recruitment targets through local advertising, media exposure for the consortium, and solid working alliances with VHA and DoD service providers. Based on our experience with numerous STRONG STAR trials and the original FORT trial, we expect <30% attrition and have factored this into our recruitment target. Participants will be reimbursed for time and travel.

4.1 Inclusion Criteria

Study participants must meet all of the inclusion criteria below to participate in this study as follows:

- 1) Demographics for inclusion in this research include both genders, all racial/ethnic groups, and ages 18-72.
- 2) Present with chronic musculoskeletal pain (CMP) as a primary pain complaint
- 3) CMP is accompanied by at least moderate disability based on a score of 20% or more on the Oswestry Disability Index;
- 4) Consistent with NIH Task Force recommendations, "chronic" CMP has been a problem for the Veteran for at least half the days in the last 3 months and was acquired or exacerbated as part of active duty U.S. military service in the Gulf War, Operations Iraqi Freedom (OIF), Enduring Freedom (OEF), or New Dawn (OND) war eras.
- 5) CMP presents in the context of comorbid psychiatric symptoms of posttraumatic stress disorder (PTSD; based on a score of 25 or more on the PTSD Checklist-Version 5) and/or depression (based on a score of 10 or more on the PHQ-9).

6) Demonstrate prior “chronic” opioid use (defined as using opioid medication for 20 out of every 30 days over three or more months) and discharged off of persistent opioid medications on their own or by a provider for at least one week prior to the pain management program period (Weeks 1-3).

7) Speak and read/understand English well enough to fully participate in the intervention and to reliably complete assessment measures.

8) The Veteran will be eligible to be a PRC patient (i.e., have multiple trauma related physical and psychological injuries; VA, 2013) and be eligible for Physical Therapy referral through the PRC (though the referral for the same service could also come from another VHA provider). All participants will be offered Physical Therapy services before enrollment and will be enrolled after completing or denying Physical Therapy.

4.2 Exclusion Criteria

All candidates meeting any of the exclusion criteria below at baseline will be excluded from study participation:

- 1) Actively engaged in an intervention or program specifically targeting opioid use (including those using naloxone).
- 2) Present with active psychosis or suicidal ideation with intent. These symptoms must be stabilized (i.e., maintained at or below moderate intensity for 6 weeks with no acute episodes requiring higher levels of intervention) through a VHA Psychology or Psychiatry referral and confirmed by the mental health provider before the Veteran is eligible to participate.
- 3) CMP is not related to or exacerbated by military service during the OEF/OIF/OND combat eras.
- 4) Present with significantly diminished decision-making capacity (e.g., severe cognitive dysfunction related to severe TBI).
- 5) Pregnant women
- 6) Inability or unwillingness of individual or legal guardian/representative to give written informed consent.

4.3 Study Enrollment Procedures

- Potential participants may be directly referred to the study by their VA provider or may directly contact the study coordinator on their own in response to flyers/pamphlets distributed at VA clinics

- Consistent with current STRONG STAR practices, we will maintain an Enrollment Log describing the timeline of screening and consent as well as the disposition and reason for enrollment/disqualification (see **Appendix A3**).
- Consent for participation in this research will take place in the South Texas Veterans Health Care System (STVHCS) PRC or on the STVHCS Barter Research Unit (BRU). Potential participants who are referred by a provider or who self-refer in response to a flyer will call the study coordinator and arrange a time to meet and discuss the study. Those who sign a **Consent to Contact** form after meeting with their physician at the STVHCS (**Appendix A1**), will receive a phone call from the study Coordinator. Participants will be asked to meet individually in a private room at the PRC/BRU with the Coordinator where they will be told about the study and will have an opportunity to ask any questions they may have of the Coordinator. Potential participants will be given a copy of the study informed consent document (ICD, **Appendix A2**) and will be allowed to take it home with them if they wish to take time to read it. Upon reading the document, the potential participants will have an opportunity to ask questions about the study and may meet with a study investigator to address their questions. Consistent with STRONG STAR procedures, the Coordinator will have a checklist of questions about the ICD that they will ask the potential participants to ensure that they understand. Once understanding is confirmed, the participants will sign the ICD and be enrolled into the study and recorded on the NCCIH Enrollment Form (**Appendix A3**). A unique identifier will be assigned to the participant using a code developed in accordance with the STRONG STAR Unique Identifier SOP (**Appendix A4**).
- Participants will be randomly assigned into one of the two study arms (FORT-A, Treatment as Usual) on a 1:1 ratio. Participants will be randomized using variable sized blocks of an even number to maintain a balance within blocks. One weakness of block randomization is that blinded study staff who are aware of established block sizes will be able to predict, with increasing certainty, how a participant will be randomized as blocks fill. This does pose a threat to blinding and creates an opportunity for non-random assignment (e.g., cherry picking a participant who may be a particularly good responder to be “randomized” into the experimental condition). To maintain a blinded assignment schedule, we have chosen to work with the STRONG STAR Biostatistics and Data Core to execute the randomization schedule, hold the blinded assignments, and administer them to the study Coordinator sequentially during enrollment (i.e., the Coordinator and study team will always remain blinded to the next assignment)

